## Research plan

The study is planned in a prospective randomized controlled design as illustrated in appendix 1 and 2 and will be carried out in close collaboration with the Department of Urology. The patients will be included and randomized as a part of one of the initial doctors appointments in a consultation room, and they will be encouraged to bring a relative to this consultation. Patients are identified when they have an appointment at Department of Urology, and the researchers will be given information from the clinicians, which means that they will not access the patient journals before enrolling. The patients will be informed about the project from the PhD-student, a physician from the Nuclear Medicine Departments, an Urologist from the cooperating departments or a nurse involved in the project, all with expertise in prostate cancer. They will be offered time to consider enrolment in the trial. The patients will be offered further information and answering of upcoming questions over the telephone after the initial talk. At this time or one of the following days, when they have accepted to be enrolled in the project and signed the written consent, they will be randomized in REDCap, where the randomisation code is kept. The randomization will be stratified according to the patients clinical risk status and pathology of biopsies. The written consents will be collected at the Nuclear Medicine Department, when they meet for their scan and at the earliest the day after the information in Department of Urology. Our study population will comprise men with a newly diagnosed intermediate or high risk (including locally advanced) PCa (1) or with a clinical suspicion of metastases based on other findings. Included patients will be randomized into a control group (A) and an interventional group (B). Group A will be staged by conventional imaging, i.e. CE-CT for N-staging and NaF-PET for M-staging. Group B will be staged by F-PSMA PET/CT for both N- and M-staging. A subset of patients with risk of extracapsular extension considered for radical prostatectomy in group B will also have an F-PSMA-PET/mpMRI-scan for T-staging (evaluation of the tumor). This scan will be performed in continuation of the F-PSMA-PET/CT, i.e. on the same administered dose of F-PSMA. Furthermore, a subgroup of patients in group B will have a blinded NaF-PET-scan for the purpose of performing comparative accuracy analyses.

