Biopsy of suspected metastatic lesions in N- and M-positive patients (suspicion of metastases) as well as lymph node specimen in N- and M-negative patients will be intended as reference standard in both groups as well as a nadir unmeasurably low post-surgery prostate specific antigen blood sample to indicate no residual disease where applicable. Reference standard in the accuracy analysis of F-PSMA PET/mpMRI with regard to T- staging is histopathology on surgical specimen. As the risk of distant metastases increases with increasing PSA-levels, analyses will be performed on both population level as a whole as well as in two PSA-strata with cut-off being PSA=100 ng/ml.

Treatment and subsequent follow-up will be planned on the basis of the results of the scans and according to current guidelines (1, 5).

Follow-up data will be collected from patient journals by the researcher/principal investigator or a delegate, and will consist of clinical information, examination reports, blood test results, information about treatments and pathology reports, all performed in a clinical setup as determined by the clinician. No extra visits, scans or blood test are required except for questionnaires. The patients will be asked to fill in questionnaires (EQ-5D-5L, FACT-P and EPIC 26) concerning quality of life during at baseline and 3, 6, 12, 24, 60, 120 og 236 months after recruitment. The questionnaires will be delivered to the patients e-boks from REDCap automatically at the specific time points. All collected information will be used in this project for analysis of treatment decision, relapse detection, overall survival and quality of life in the two patient groups.

Primary endpoints (Group A vs. B)

1. Treatment strategies and progression-free survival
2. Quality of life measures

Secondary endpoints

1. Overall survival (Group A vs. B)
2.  $^{18}\text{F}$ -PSMA-PET/MR for evaluation of extension of tumor in the prostate gland and surrounding structures compared to histopathology on surgical specimen.
3. Accuracy of  $^{18}\text{F}$ -PSMA-PET/CT compared to NaF-PET/CT for evaluation of bone metastases

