Four publications are planned, cf. section "Planned publications" below. Studies 1 and 4 will address the presumed patient benefit from staging with  $^{18}\text{F}$ -PSMA PET/CT in a randomized design, and outcome measures will consequently be impact on stage migration, treatment decision, progression free survival, and time to relapse in group A vs. group B. As studies 2 and 3 are comparative studies, outcome measures in this setting will be accuracy measures regarding N- and M-staging in study 2, and T- and R-staging as well as change in treatment intend in study 3.

Beyond the scope of this PhD-project we plan a follow-up time period of up to 20 years for analysis of disease free period, overall survival and quality of life.

Admittance to documents and data including patients journals are given to the relevant GCP-units and the Danish Medicines Agency for monitoring, audition and inspection of the project.

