## Feasibility

Patient recruitment will be performed in collaboration with relevant departments of urology in RSD. One or more parallel PhD-projects on the same study population, but nested in the Department of Urology, OUH, is planned, thereby enabling patient recruitment on either of the two departments in close cooperation. It is considered achievable to include the required 448 patients in this setting.

The Department of Nuclear Medicine, OUH, received approval to produce  $^{18}\text{F}$ -PSMA-1007 from the Danish Medicines Agency in 2019.  $^{18}\text{F}$  will routinely be produced on our two cyclotrons, and our well-equipped radiochemistry is trained in the production and labelling of a wide variety of PET-tracers complying with Good Manufacturing Practice (GMP). The tracers will be shipped to the cooperating departments. We currently have five state-of-the-art PET/CT-scanners and a PET/MRI-scanner, and will as such have all the

prerequisites for tracer production and performing the planned scans together with the cooperating Nuclear Medicine Departments.

The PSMA-PET scans performed in OUH will be evaluated and documented as in clinical practice by the applicant and three supervisors as well as a PhD student from another PhD-project - all being Nuclear Medicine specialists along with specialists in radiology, and the same set-up is planned in the cooperating departments. Conventional scans will be evaluated as part of the daily routine at the Departments of Nuclear Medicine (NaF-PET) and Radiology (CE-CT, mpMRI). The SharePoint and RedCap systems will be used for data collection and management in line with the European data protection regulation (GDPR) implemented by May 25 2018. Sharepoint will be used for safe storage of permissions and registrations, and REDCap for patient data.

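### PET/mpMRI T-staging accuracy is verified only in men who are operated on, and the scan may help decide who that is; the accuracy estimates can be biased, and the plan neither shows nor examines this

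*Combined protocol and SAP*

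**What the plan says.** All of the following is in the Research plan section of the combined protocol and SAP unless another section is named.

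- **Who is scanned.** "A subset of patients with risk of extracapsular extension considered for radical prostatectomy in group B will also have an" 18F-PSMA PET/mpMRI scan for T-staging, in continuation of the PSMA-PET/CT.
- **Reference standard.** For 18F-PSMA "PET/mpMRI with regard to T- staging is histopathology on surgical specimen". Secondary endpoint 2 repeats this: PSMA-PET/MR is assessed "for evaluation of extension of tumor in the prostate gland and surrounding structures compared to histopathology on surgical specimen". For N- and M-staging the plan names biopsy, lymph node specimens and post-surgery PSA. For T-staging it names nothing for men without a specimen.
- **Link to treatment.** "Treatment and subsequent follow-up will be planned on the basis of the results of the scans" and in line with current guidelines.
- **Study 3 outcomes.** These are "T- and R-staging as well as change in treatment intend in study 3".
- **Blinding.** The only scan called blinded is the NaF-PET: "a subgroup of patients in group B will have a blinded NaF-PET-scan". Under Feasibility, PSMA-PET scans at OUH are "evaluated and documented as in clinical practice", and the cooperating departments are to work the same way.
- **Missing data.** The section Sample size and statistical analyses commits to reporting missing data and the reasons why data are not used. It gives no analysis for scanned men without a reference standard. Its one accuracy sample size (128 patients) concerns metastases on PSMA-PET/CT against conventional imaging, not PET/mpMRI.

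**The concern.** Men enter the PET/mpMRI subset before the decision to operate is final, and the scan can influence that decision. A man whose scan suggests extracapsular extension and who is then treated without surgery has no specimen, so he cannot appear in the T-staging accuracy table. A man whose scan looks organ-confined is more likely to be operated on and to stay in it. This is partial verification. When the index test itself drives verification, the accuracy estimated in verified men differs from the accuracy in all tested men.

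At stake is what secondary endpoint 2 and the T-staging part of study 3 can conclude. The result would describe men still operated on after a known scan, yet could be read as T-staging accuracy in all men considered for surgery. The more the T reading alters the choice of surgery, the larger the gap between the two.

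**Working it through.** The documents give no sensitivity, specificity, prevalence, sample size or operation rate for PET/mpMRI, so there is no planned figure to reproduce. Every number below is an assumption chosen to show the range.

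**1. Surgery depends on the T reading.** Let Se and Sp be the true values for extracapsular extension, and let v+ and v− be the shares of T-positive and T-negative men who are operated on. In operated men:

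- apparent sensitivity = Se·v+ / (Se·v+ + (1 − Se)·v−)
- apparent specificity = Sp·v− / (Sp·v− + (1 − Sp)·v+)

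Prevalence cancels. With Se = 0.70 and Sp = 0.80:

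| v+ | v− | Apparent sensitivity | Apparent specificity |
|---|---|---|---|
| 0.95 | 0.95 | 0.70 | 0.80 |
| 0.90 | 0.95 | 0.630 / (0.630 + 0.285) = 0.689 | 0.760 / (0.760 + 0.180) = 0.809 |
| 0.75 | 0.95 | 0.525 / (0.525 + 0.285) = 0.648 | 0.760 / (0.760 + 0.150) = 0.835 |
| 0.50 | 0.90 | 0.350 / (0.350 + 0.270) = 0.565 (0.5645 before rounding) | 0.720 / (0.720 + 0.100) = 0.878 |

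Other assumed true values behave the same way. With 75% and 95% operated on, 0.60/0.80 becomes 0.542/0.835 and 0.80/0.90 becomes 0.759/0.919.

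**2. Whether a correction works in that case.** Take the third row with a prevalence of 0.40. T-positives are 0.40 × 0.70 + 0.60 × 0.20 = 0.40 of scanned men. Surgery depends only on the reading, so the predictive values in operated men are unbiased: PPV = 0.28/0.40 = 0.70 and NPV = 0.48/0.60 = 0.80. Begg-Greenes then gives:

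- sensitivity = 0.70 × 0.40 / (0.70 × 0.40 + 0.20 × 0.60) = 0.28/0.40 = 0.70
- specificity = 0.80 × 0.60 / (0.80 × 0.60 + 0.30 × 0.40) = 0.48/0.60 = 0.80

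The true values return, but only if the reading and surgery status of every scanned man are kept.

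**3. Surgery depends on the N/M result instead.** N- and M-staging belong to the PSMA-PET/CT done in the same session. Assume prevalence 0.50, Se/Sp 0.70/0.80, N/M-positive in 30% of men with extension and 5% without (independent of the T reading given true T stage), and surgery in 30% of N/M-positive and 95% of N/M-negative men.

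- Operated on, with extension: 0.30 × 0.30 + 0.70 × 0.95 = 0.755
- Operated on, without extension: 0.05 × 0.30 + 0.95 × 0.95 = 0.9175
- Operated on among T-positives: (0.35 × 0.755 + 0.10 × 0.9175) / 0.45 = 0.356/0.45 = 0.79
- Operated on among T-negatives: (0.15 × 0.755 + 0.40 × 0.9175) / 0.55 = 0.48025/0.55 = 0.87
- Raw sensitivity: 0.26425 / (0.26425 + 0.11325) = 0.70
- Raw specificity: 0.36700 / (0.36700 + 0.09175) = 0.80

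Surgery rates differ by T reading, yet the raw estimates are unbiased. Begg-Greenes on the T reading alone uses PPV = 0.26425/0.356 = 0.742 and NPV = 0.367/0.48025 = 0.764:

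- sensitivity = 0.742 × 0.45 / (0.742 × 0.45 + 0.236 × 0.55) = 0.72
- specificity = 0.764 × 0.55 / (0.764 × 0.55 + 0.258 × 0.45) = 0.78

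Here the correction introduces a small bias. Any correction must therefore also condition on the N/M result.

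**The case against.** Several counter-arguments carry weight.

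- **T findings may change how surgery is done and not whether it is done.** The Background section ties mpMRI to planning the resection level before prostatectomy, and R-staging is a study 3 outcome. If that is its main use, the bias is small or absent. This stands as a limit on size. It does not remove the point, because the hypothesis predicts that better local staging will change treatment strategy, and study 3 measures change in treatment intent.
- **The scan is not the only determinant.** Treatment also follows guidelines, and N/M findings may explain much of any switching. This also stands: step 3 shows that such switching need not bias the raw estimates.
- **The plan already covers part of this.** It promises to report missing data and reasons for unused data, and endpoint 2 names the surgical specimen. That does not amount to a count by scan result, a statement of the target population, or an analysis of unverified men.
- **The specimen is the natural reference standard.** Agreed; nothing here asks to replace it or to alter care.
- **Only a secondary endpoint in a subset of one arm is affected.** Correct; no primary endpoint is touched.

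A reader might infer that the accuracy estimates are certain to be biased, or that men switched away from surgery are lost to the trial. The documents support neither. The bias is conditional on the T reading influencing surgery, and switched men still count for change in treatment intent; they are missing only from the accuracy table.

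**Conclusion.** The point holds as a conditional one. The plan sets up every condition for partial verification bias in PET/mpMRI T-staging accuracy: scanning before the decision, no stated blinding, results used in planning treatment, and a reference standard only in operated men. It includes no analysis that would reveal or bound the bias.

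If T-positive men are operated on less often because of the T reading, sensitivity is understated and specificity overstated. On the assumed values, the shift in sensitivity runs from about 1 point (0.70 − 0.689) to about 14 points (0.70 − 0.5645), and in specificity from about 1 point (0.809 − 0.80) to about 8 points (0.878 − 0.80). It is zero if surgery does not depend on the T reading given true T stage. The documents do not say which case is closer.

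It would also be tempting to conclude that a corrected estimate should replace the raw one as the main result. That is not supported, since a correction on the T reading alone can itself mislead. The point warrants a change because the remedy is cheap and alters what endpoint 2 can claim.

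**What to change.** Add to the Research plan (reference standard and secondary endpoint 2) and to the section Sample size and statistical analyses:

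1. Report every man who had PET/mpMRI, cross-tabulated by T reading, PET/CT N/M result and whether he was operated on.
2. Keep the raw sensitivity and specificity table, and state that it is accuracy in operated men and not in all men considered for surgery.
3. Prespecify, as a sensitivity analysis and not as the main estimate, a partial-verification correction (Begg-Greenes, inverse-probability-of-verification weighting or multiple imputation). It should condition on the T reading and the PET/CT N/M result, plus PSA, Gleason score and clinical T stage where numbers allow, with bootstrap confidence intervals.
4. Give best-case and worst-case bounds for unverified men: all their T readings counted as right, then all counted as wrong.

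No new procedure is needed. Examination reports, treatment and pathology are already to be collected, and PSA, Gleason score and clinical T stage are eligibility items in Appendix 1. The cost is some programming, wider intervals, possibly unstable weights in a subset of unstated size, and reliance on the assumption that surgery depends only on recorded variables.

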## Sample size and statistical analyses

Assuming that staging intermediate and high risk PCa with  $^{18}\text{F}$ -PSMA PET/CT leads to upstaging in 20%, 398 patients, i.e. 199 patients in each arm, will be necessary to estimate the proportion of upstaged patients with  $^{18}\text{F}$ -PSMA PET/CT with sufficient precision as the expected length of the Wilson-score 95% CI for this proportion will be 11% (simulation study with N=2000 trials). These numbers are sufficient to indicate that the proportion of upstaged patients with  $^{18}\text{F}$ -PSMA PET/CT is statistically significantly larger than 12.9%

under above assumptions (power: 80%; two-sided testing; Type I error: 5%). A total of 448 patients (224 in each arm) are sufficient to indicate a statistically significant difference in progression free survival with assumed hazard rates of 0.35 and 0.5 for 18F-PSMA PET/CT and conventional staging respectively, implying a hazard ratio of 0.7. Estimates are based on a study duration of 4 years, consisting of 3 years accrual time and minimum follow-up period of 1 year before the first data collection, and a loss-to-follow-up of 10% (two-sample comparison of survivor functions; Exponential test; Type I error: 5%). Therefore, **448 patients (224 in each arm)** will be included in the study. For sample size calculation for the accuracy analyses planned in Group B only, we assumed a prevalence of metastases of 30%, sensitivity and specificity of 0.38 and 0.91 for conventional imaging, and 0.85 and 0.98 for PSMA-PET/CT. Then, a sample size of **128 patients** is sufficient to indicate a superior sensitivity for PSMA-PET/CT and a non-inferior specificity for PSMA-PET/CT, with a non-inferiority margin of 0.052, at a significance level of 5% (two-sided) with a power of 80%. We expect 224 patients from OUH, 80 patients from Hospital of Little Belt, 72 patients from Hospital of South West Jutland and 72 patients from Hospital Sønderjylland. Patients from Hospital Sønderjylland will have their scans performed in either Hospital of Little Belt or OUH Odense.

Primary analyses will be done as indicated in the sample size rationale above. Cox proportional hazard regressions will be adjusted for available demographic and clinical baseline variables, and graphical displays will comprise Kaplan-Meier plots including risk tables (i.e. patients at risk in each group).

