Descriptive statistics will be done according to data type (mean±SD or median (range) for symmetrically and unsymmetrically distributed continuous variables, respectively, as judged visually with histograms including approximating Normal curves; frequencies and percentages for categorical variables). Exploratory, bivariate testing will be done with unpaired t-tests or, alternatively, Wilcoxon's rank sum test on continuous and Chi-squared test, alternatively, Fisher's exact test for categorical variables. Level of significance will be 5%. All analyses will be done with STATA/IC 15 (StataCorp, College Station, Texas 77845 USA). If exceptions for this statistical plan is needed, it will be reported when published.

Missing data will be reported in the publications. Illegitimate data will be excluded. Reason for un-used data will be reported.

The primary analysis of QoL and morbidity will be based on the changes in the FACT-P questionnaire at the timepoints: inclusion and 12 months. An 8-point decline in the global FACT-P score will be considered clinically relevant. The secondary analyses include the group difference in a repeated measurement analysis, making use of data collected at the several time points of FACT-P. Secondary analyses will likewise be conducted using the EQ-5D-5 and EPIC-26. The time from baseline to decline of 8 points in global FACT-P score will be visualized by Kaplan-Meier plots and explored with a two-sided log-rank test. The level of significance will be 5%. All analyses will be done with STATA/IC 15 (StataCorp, College Station, Texas 77845 USA).

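### Results are to be analysed separately below and above PSA 100 ng/ml with no test of whether the effect differs by PSA, so discordant strata could be misread

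*Combined protocol and SAP*

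**What the plan says.** In the Research plan, at the end of the paragraph on the reference standard, the protocol states that "analyses will be performed on both population level as a whole as well as in two PSA-strata with cut-off being PSA=100 ng/ml". The reason given is "As the risk of distant metastases increases with increasing PSA-levels". No endpoint, test or significance level is attached to this sentence.

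Under Sample size and statistical analyses, the primary analyses are tied to the sample-size rationale. That rationale covers undivided groups: 448 patients (224 per arm) for progression-free survival and 128 patients for the Group B accuracy study. A general 5% significance level is set, and the planned Cox models are adjusted for baseline variables. No arm-by-PSA term is mentioned.

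On allocation, "The randomization will be stratified according to the patients clinical risk status and pathology of biopsies". A cut at PSA 100 ng/ml is not named there.

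**The concern.** With results from two strata side by side, a reader will ask whether the scan matters more in one than in the other. Two separate p values do not answer that. One stratum can be significant and the other not because they differ in size, or by chance, while the true effect is the same. The plan has no rule for reading such a pattern.

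At stake is a published statement that staging with PSMA-PET/CT helps, or is more accurate, only on one side of 100 ng/ml. Such a statement could influence which men are offered the scan.

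**Working it through.** Progression-free survival serves as the illustration because the protocol gives enough inputs for it.

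**Inputs from Sample size and statistical analyses.** "assumed hazard rates of 0.35 and 0.5 for 18F-PSMA PET/CT and conventional staging respectively, implying a hazard ratio of 0.7"; 3 years' accrual and 4 years in total; 10% loss; 448 patients, 1:1; exponential test at 5%.

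**Assumptions.** Two-sided testing and 80% power are stated for the upstaging calculation and taken to apply here too. The share *f* of events above PSA 100 is not in the documents and is varied from 5% to 50%. Each stratum is taken to be tested at two-sided 5%, the plan's only stated level.

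**Step 1: reproduce 448.** With uniform accrual, the event probability at hazard λ is P(λ) = 1 − [exp(−λ) − exp(−4λ)]/(3λ).
- P(0.35) = 0.564, P(0.50) = 0.686, and P(0.425) = 0.631 at the mean hazard.
- The exponential (hazard-difference) test needs n per arm = {1.96·√(2·0.425²/0.631) + 0.842·√(0.35²/0.564 + 0.50²/0.686)}² / 0.15² = 200.8, so 201.
- Allowing for loss, 201/0.90 = 223.3, so 224 per arm and 448 in total. The stated figure reproduces. At 90% power the same approach gives about 600, so 80% is the implied power.

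**Step 2: overall signal.**
- Expected events: 448 × 0.90 × 0.625 ≈ 252.
- Mean overall z: √(252/4) × |ln 0.7| = 2.83.
- Power: Φ(2.83 − 1.96) = 81%.

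**Step 3: same hazard ratio of 0.7 in both strata.** The mean z is 2.83·√f above PSA 100 and 2.83·√(1−f) below. The strata are independent, so P(exactly one significant) = p₁(1−p₂) + p₂(1−p₁). The last two columns come from simulation with 2,000,000 draws, counting both tails.

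| Share of events above PSA 100 | Power, high stratum | Power, low stratum | Exactly one significant | Exactly one significant and interaction p<0.05 |
|---|---|---|---|---|
| 5% | 9% | 79% | 73% | 3.0% |
| 20% | 24% | 72% | 61% | 4.1% |
| 50% | 52% | 52% | 50% | 4.9% |

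By hand for 20%: 0.244 × 0.284 + 0.716 × 0.756 = 0.069 + 0.541 = 0.61.

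**Step 4: no true effect.** The chance of at least one significant stratum is 1 − 0.95² = 9.75%. The overall statistic is √f·z₁ + √(1−f)·z₂, and simulation gives at least one of the three tests significant in 10.6% to 11.5% of trials. Removing the overall test's own 5% leaves 5.6% to 6.5% in which a stratum is significant and the overall test is not.

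**Step 5: power of the interaction test.** If the hazard ratio is 0.7 in one stratum and 1.0 in the other, power is Φ(2.83·√(f(1−f)) − 1.96). This is 9% at *f* = 5% and 29% at *f* = 50%.

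**If only accuracy is meant.** The 128 patients at the assumed 30% prevalence give 128 × 0.30 ≈ 38 men with metastases before any split. Stratum estimates of sensitivity would rest on fewer still.

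**The case against.** The strongest reply is that the plan already settles what is primary. Its primary analyses follow the sample-size rationale, which concerns undivided groups, and no stratum has a sample size, power or hypothesis. That stands. A reader might infer that every endpoint is tested three times at 5% and that the false-positive rate of the primary analyses rises. The documents do not support this: the stratum sentence names neither endpoints nor a level, and the primary tests keep their own 5%.

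The sentence also closes a paragraph on the reference standard, and its reason concerns how common metastases are. Reporting accuracy by stratum is a natural reading. Nothing restricts it to accuracy, however, and the difficulty of comparing strata is the same there. Nor does the plan state a hypothesis that the effect changes with PSA; that too would be an inference.

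The discordance in Step 3 mostly reflects low power in the smaller stratum. The overall test is also significant in more than nine in ten of those trials, and discordance with a non-significant overall result occurs in only about 3% to 4% of all trials. This limits the harm, since a reader would have to set aside the main result. It does not prevent a claim that the overall benefit is confined to one stratum.

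The cut-off is single, prespecified and reasoned, so a data-driven cut-point is not at issue. It would also go too far to say that PSA plays no part in randomisation: clinical risk status is undefined and may include it. Only the cut at 100 ng/ml is not named.

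**Conclusion.** The point holds as a weakness in how stratum results could be read, not as a flaw in the primary analyses. With an identical effect in both strata, exactly one would be significant in about 50% to 73% of trials. If a significant interaction is also required, this falls to about 3% to 5%. With no effect, the extra chance of a significant stratum beside a non-significant overall test is about 6%.

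These figures rest on progression-free survival as the example, about 252 events, two-sided 5% testing in each stratum, and an assumed 5% to 50% of events above PSA 100. The size varies over that range; the conclusion does not. The figures do not carry over directly to the paired accuracy analysis, although the logic does.

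**What to change.** - State which endpoints are analysed by PSA, and say that these analyses are exploratory.
- Judge any difference by one arm-by-PSA interaction term per endpoint, or a modality-by-PSA term for the paired Group B accuracy analysis. Continuous log PSA is preferable to the dichotomy, with a check that a linear term is adequate.
- Report estimates with 95% confidence intervals on each side of 100 ng/ml, and base no claim on a single stratum's p value.

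The cost is a few sentences and one model term per endpoint. PSA is already an eligibility variable, so no new data are needed. The paired accuracy model takes somewhat more work, with only about 38 men expected to have metastases. The drawback is low power, about 9% to 29% in the two-stratum example. The text should therefore say that a non-significant interaction does not show that the effect is the same in both strata.

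### PFS and quality of life are both primary A-vs-B endpoints at 5%, and no rule says which result, or combination of results, counts as success

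*Combined protocol and SAP*

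**What the plan says.** Under "Primary endpoints (Group A vs. B" (closing bracket omitted), the Research plan has two numbered items: "Treatment strategies and progression-free survival" and "Quality of life measures". The numbers are not described as a testing order.

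The section Sample size and statistical analyses treats them as follows.

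- **PFS.** The 448 patients come from hazards of 0.35 and 0.5, with the basis given as "two-sample comparison of survivor functions; Exponential test; Type I error: 5" per cent. Timing is 3 years of accrual plus a "minimum follow-up period of 1 year before the first data collection". An adjusted Cox regression is also mentioned.
- **Quality of life.** The primary analysis uses change in FACT-P between inclusion and 12 months. The level is 5%, stated once for the analyses generally and again at the end of the quality-of-life paragraph. There is no sample size or power calculation.
- **Between-group tests.** t-test or Wilcoxon, and Chi-squared or Fisher, are listed for exploratory two-variable comparisons. None is expressly assigned to the primary FACT-P comparison or to treatment strategy.
- **Upstaging.** A one-sample test is sized to show a proportion "statistically significantly larger than 12.9" per cent. Upstaging is not on the primary endpoint list.

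The section adds: "Primary analyses will be done as indicated in the sample size rationale above". That rationale contains no joint rule. Of the four planned publications, the first covers treatment strategy and the fourth PFS; none covers quality of life.

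**The concern.** Two endpoints of equal stated rank compare the same randomised arms, each with the whole 5%. The plan does not say what the trial concludes if PFS is significant and FACT-P is not, or the reverse. The rule could be that either one suffices, that both are needed, or that PFS decides. These rules have different error rates and different power, and the choice would be open after the results are known. Under the first of them, the error attached to a primary claim is nearly double the stated level.

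**Working it through.** **Inputs.** From the statistical section: hazards 0.35 and 0.5, 3 years accrual, 1 year minimum follow-up, 10% loss, type I error 5%, 224 per arm. Assumed: two-sided testing and 80% power for PFS (both stated there for upstaging, neither for PFS), uniform accrual, the correlations between tests, and FACT-P power.

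**1. Reproduce 448.** The probability of an event is p(λ) = 1 − [exp(−λ) − exp(−4λ)]/(3λ). This gives p(0.35) = 0.564, p(0.5) = 0.686 and, at the mean hazard, p(0.425) = 0.631.

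For the exponential test on the hazard difference:
- V0 = 2 × 0.425²/0.631 = 0.573
- V1 = 0.35²/0.564 + 0.5²/0.686 = 0.582
- n per arm = (1.960 × √0.573 + 0.842 × √0.582)²/0.15² = 200.8
- 200.8/0.9 = 223.1, so 224 per arm and 448 in total, as stated.

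The same formula gives 512 at 85% power and 600 at 90%. So 448 implies about 80% power, with the full 5% spent on PFS.

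**2. Chance of at least one false primary result, both nulls true, each test at two-sided 5%.** With independent tests:
- either direction: 1 − 0.95² = 9.75%
- in favour of PSMA: 1 − 0.975² = 4.94%

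The correlated cases use the bivariate normal distribution.

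| Correlation (assumed) | Either direction | In favour of PSMA |
|---|---|---|
| 0 | 9.8% | 4.9% |
| 0.3 | 9.5% | 4.8% |
| 0.5 | 9.1% | 4.5% |
| One test only | 5% | 2.5% |

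**3. What each possible rule does to PFS at 448.** Power = Φ[(0.15 × √201.6 − z × √V0)/√V1], where 201.6 = 224 × 0.9.
- *Fixed sequence, PFS first:* PFS keeps 5%; power 80.2%.
- *Equal split, 2.5% each:* power 71.5%; restoring 80% needs 542 patients.
- *Holm over PFS and FACT-P:* PFS power = 0.715 + (0.802 − 0.715) × Q, where Q is FACT-P power at 2.5%. FACT-P power of 0.5, 0.8 and 0.9 at 5% corresponds to Q of 0.389, 0.712 and 0.841. PFS power is then 74.9%, 77.7% and 78.8% (independent tests).

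**4. What each rule does to FACT-P, at an assumed 80% power.** Fixed sequence: 0.802 × 0.8 = 64%. Holm: 0.712 + (0.8 − 0.712) × 0.715 = 77.5%.

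**5. Timing.** The last patient enters at year 3, so the last 12-month FACT-P falls due at year 4, together with the first PFS data collection.

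**The case against.** The best counter-argument is that PFS plainly leads. The overall aim and hypothesis name accuracy, treatment strategy and PFS, not quality of life. PFS sets the sample size. Quality of life is absent from the outcome measures given where the plan says "Studies 1 and 4 will address the presumed patient benefit from staging", and from all four planned publications. The primary FACT-P analysis could mean primary within the quality-of-life domain. These signals make a claim resting on FACT-P alone less likely, but they do not settle the matter: the Research plan still numbers quality of life as a primary endpoint, and the hierarchy is nowhere stated.

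The second counter-argument is that the inflation is conditional. If both endpoints must succeed, no adjustment is needed. If they answer separate questions, each is held at 5%. That is correct, and it limits the claim made here. The plan adopts none of these rules.

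Three stronger readings are tempting, and the documents do not support them.

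- A reader might infer that the trial's type I error simply is 9.8%. It is so only if either result alone counts as success, which no section says.
- A reader might count upstaging as a third primary test, giving 1 − 0.95³ = 14.3%. That test is one-sample, does not compare A with B, and is not on the endpoint list. Only the general sentence on primary analyses could bring it in.
- A reader might say that the plan has no between-group test for FACT-P or treatment strategy. Suitable tests are listed, but as exploratory; what is missing is their assignment to the primary comparisons.

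**Conclusion.** The point holds in limited form. Two primary A-vs-B endpoints each carry 5%, and no success rule is stated. On an either-one-suffices reading, the chance of at least one false primary result is about 9.8% in either direction and 4.9% in favour of PSMA, slightly less if the two tests are positively correlated. These error rates rest on both nulls being true and, for the correlated figures, on assumed correlations. The 80% PFS power is inferred from reproducing 448, and the Holm and FACT-P power figures are illustrations, because the documents give no FACT-P standard deviation, expected difference or power. The trial stays interpretable if the rule is fixed in time, so this should be corrected but does not undermine the design.

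**What to change.** Before any A-vs-B outcome data are analysed, write one decision rule into the plan. The simplest is a fixed sequence:

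1. PFS in all randomised patients at the first data collection, two-sided 5%, with one named test. The section mentions both an exponential test and an adjusted Cox model. Choose one and, if covariates are used, list them in advance.
2. Only if PFS is significant, the between-group difference in 12-month FACT-P, two-sided 5%, by a named method, for example a linear model with arm, baseline FACT-P and the randomisation strata.

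Treatment strategy is part of the first listed endpoint, so the sponsor should either give it a later step with its own named test or report it as estimates with 95% confidence intervals. Report upstaging as an estimate with a 95% confidence interval.

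The cost is a few lines of wording, with no extra patients and no delay. The sample size of 448 and the inferred PFS power of about 80% are unchanged. The downside is that FACT-P is confirmatory only if PFS succeeds. If the sponsor wants quality of life to stand on its own, Holm over the two endpoints is valid at the same sample size, with PFS power of about 75% to 79% under assumed FACT-P power of 50% to 90% and independence. An equal split is also valid but costs more PFS power, as shown in the working.
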